## 6.2 Study Baseline Assessments

### 6.2.1 Screening

1. Informed consent
2. Inclusion and exclusion criteria
3. Demographic and admission data (including age, sex, race/ethnicity, pre-hospitalization level of care (according to ECOG/WHO Performance Status classification):
  - 0: able to carry out all normal activity without restriction
  - 1: restricted in strenuous activity but ambulatory and able to carry out light work
  - 2: ambulatory and capable of all self-care but unable to carry out any work activities; up and about more than 50% of waking hours
  - 3: symptomatic and in chair or in bed for greater than 50% of the day but not bedridden
  - 4: completely disabled; cannot carry out any self-care; totally confined to bed or chair
4. Medical history, including information on COVID-19 vaccination
5. Physical examination
6. Pregnancy test for women of reproductive age, if not performed in routine clinical care
7. Documentation of lung X-ray / CT scan (if available as part of standard clinical care), COVID-19 disease history (symptom onset, confirmatory SARS-CoV-2 test done, hospital admission date and time), Previous (7 days prior to arrival to hospital) and concomitant medications. Note that use of systemic glucocorticoids, baricitinib or tofacitinib (or other JAK-STAT signalling pathway inhibitors) seven days before hospital admission and at randomization is an exclusion criteria.
8. Adverse events

### 6.2.2 Pre-dose D1

1. Inclusion and exclusion criteria
2. Randomization (if feasible can be done also during screening)
3. Specimen collection including genetic sample per [Table 2](#).
4. COVID-19 specimen collection (blood sample and nasopharyngeal swab)
5. WHO 9-point ordinal scale
6. Concomitant medications and therapies. Note that use of systemic glucocorticoids, baricitinib and tofacitinib (or other JAK-STAT signalling pathway inhibitors) at randomization is an exclusion criteria
7. Clinical status assessments
8. Vital signs
9. Adverse events

Screening assessments will be carried out after informed consent has been obtained and must be completed before the first dose of the study drug is administered. If a patient continues to meet all entry criteria (including negative pregnancy test and not receiving systemic glucocorticoids, baricitinib or tofacitinib (or other JAK-STAT signalling pathway inhibitors)), study drug will be administered. The first dose of study drug must be administered within 48 hours of admission to hospital, preferably as soon as possible.

The specimen collections and assessments at pre-dose D1 should be within 4 hours prior to the administration of study drug.

### 6.3 Study Assessments During Hospital stay

The following in-hospital data will be collected to assess trial efficacy and safety endpoints. Most data may be assessed by medical record review.

1. Administration of study drug once daily for 6 days
2. Close monitoring of vital signs for the 60 minutes following study drug administration
3. Specimen collection including COVID-19 sample per [Table 2](#).
4. WHO 9-point ordinal scale
5. Concomitant medications and therapies
6. Clinical status assessments
7. Adverse events
8. Hospital discharge disposition.

The specimen collection should be prior to the administration of study drug and within +/-2 hours of the sampling time at D1.

If a subject has been discharged from the hospital but is re-admitted before Day 28 to the study site for COVID-19 associated reasons, the data for the visits assessments are recorded in CRF. Laboratory samples are not taken from re-admitted subjects, but, if possible, a serum sample for determining the viral load should be taken according to the timepoints in [Table 2](#). The re-admission to hospital is reported as a SAE.

### 6.3.1 Vital Signs

Vital signs will be measured supine pre-dose on D1 (baseline) and daily while hospitalized as detailed in the Schedule of Procedures ([Section 6, Table 2](#)). The date and time of collection of each parameter will be recorded in the e-CRF.

Vital sign variables are:

- Blood pressure (BP; systolic, diastolic and mean; mmHg)
- Heart rate (HR; bpm): measured as per clinical practice in each hospital
- Total respiratory rate (breaths per minute)
- Temperature (°C): core temperature to be measured according to the site's usual practices for temperature recording and the site used for measurement should be recorded in the e-CRF

### 6.3.2 Physical Examinations

Physical examinations will be performed in accordance with the Schedule of Procedures ([Table 2](#)) and as applicable to subjects' condition.

A physical examination covering the major body systems (general appearance, head [ear, nose and throat], cardiovascular, eyes, respiratory, abdomen, urogenital, musculoskeletal, neurological, lymph nodes and skin) will be performed at screening (baseline) and following according to standard clinical practice and at D28 or Day of discharge from hospital (whichever is earlier).

At screening the physical examination will also include:

- Actual body weight measured or provided by the subject
- Actual height measured or provided by the subject.

### 6.3.3 Clinical status assessments

Clinical status assessments include survival, hospital status, ICU status, renal support, ECMO, oxygen support, and mechanical ventilation. Assessments for D14 and D28 are made by phone for non-hospitalized subjects. On D90 only survival and hospital status will be collected. Information will be sought from health records if patient cannot be contacted by phone.

### 6.3.4 Hospital Laboratory Assessments

#### 6.3.4.1 Biochemistry and Haematology

The biochemistry and haematology analysis will be performed at the hospital laboratories of the individual Investigator sites. Copies of laboratory accreditation and relevant reference ranges will be provided to the Sponsor or representative prior to the analysis of the first patient sample at that site.

The laboratory variables measured in the study will be as detailed in [Table 3](#).

Blood samples for determination of biochemistry and haematology (CBC, WBC Differential) will be taken at pre-dose on D1 (baseline value), D2-D7, D10 and D14 while the patient is in the hospital, and on D28 or the last day in hospital. The date and time of sample collection and the results will be recorded in the e-CRF (results for analysis performed routinely at the site on other days will also be recorded in eCRF).

FP-1201-lyo 10 µg powder for solution for injection  
(lyophilized human interferon beta-1a)

page 40 (60)

**Table 3. Biochemistry and haematology variables**

Haematology:	Haemoglobin Haematocrit Erythrocytes MCV Platelets Leukocytes Differential counts of: Neutrophils Eosinophils Basophils Lymphocytes Monocytes	Biochemistry:	Albumin Creatine kinase Creatinine Bilirubin Alkaline phosphatase AST ALT Lactate Sodium (blood gas value acceptable) Potassium Bicarbonate Calcium (total calcium corrected for albumin level)
--------------	--	---------------	--

Pregnancy test: In women with child-bearing potential only. A urine pregnancy test will be performed unless the patient is not producing urine in which case a serum pregnancy test will be performed instead

*Abbreviations: AST=aspartate transaminase; ALT=alanine transaminase; MCV=mean corpuscular volume.*

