## 2.4 Dexamethasone

### 2.4.1 Clinical safety experience of Dexamethasone

I.V dexamethasone is recommended therapy for hospitalized patients with hypoxemia who are receiving oxygen through a high-flow device, or non-invasive ventilation, or invasive ventilation. It is also recommended for patients receiving increasing amounts of supplemental oxygen therapy (<https://www.covid19treatmentguidelines.nih.gov/therapies/immunomodulators/corticosteroids/>). It has been proposed that the potent anti-inflammatory effects of corticosteroids might prevent or mitigate the deleterious systemic inflammatory effects in patients with severe form of COVID-19.

The incidence of side effects associated with the use of dexamethasone generally correlates with dosage, timing of administration, and duration of treatment. The most commonly occurring side effects of dexamethasone have included a wide range of psychiatric reactions, psychotic reactions, behavioural disturbances, irritability, anxiety, sleep disturbances and cognitive dysfunction including confusion and amnesia, decreased blood eosinophils and lymphocytes, increased infection susceptibility, masking of infection signs, aggravated infection, and fungal infections of mucous membranes and the skin. In adults the frequency of severe reactions has been estimated to be 5-6%.

In this study, 6 mg IV doses of dexamethasone will be administered for 6 days. Adverse reactions associated with the use of glucocorticoids are usually dependent on the dose and the duration of the

treatment. Treatment duration of 6 days is relatively short, and the occurrence of the above-mentioned reactions associated with long-term use is unlikely.

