Phase III clinical studies (INTEREST and MR11A8-2) and phase I clinical study (FP1CLI011) in healthy volunteers did not identify any major safety risks for FP-1201-lyo. A decrease in IL-6 IL-8 and IFN-gamma values was observed in patients treated with FP-1201-lyo, a finding that was similar to those found in a placebo group (Ranieri et al. 2020). Fever was the most common AE in phase III studies, and all healthy volunteers in the study FP1CLI011 experienced fever as a response to the treatment. The pyrogenic effect is characteristic for IFN beta-1a as well as for other type I IFNs. In healthy volunteers, the body temperature characteristically reached 38–39°C (axillary) 1-2 hours after the FP-1201-lyo administration, and this elevation persisted for around 2 hours (all treated with antipyretic analgesics). The temperature elevations vary substantially among individuals. IFN beta-1a induced fever responds to antipyretic analgesic drugs, which are recommended to decrease (or prevent) the flu-like symptoms associated with IFN beta-1a administration. Serious adverse reactions possibly related to IFN beta-1a reported more than once in phase III clinical trials, include two cases of increased transaminases, two cases of thrombocytopenia, three cases of hypertension, and two cases of rhabdomyolysis. The available information suggests that the present study's risk/benefit ratio is favourable.

Investigating the effect of IFN beta-1a to prevent ARDS in viral pneumonia (and particularly SARS-CoV-2) is especially intriguing because of the potential beneficial effects of IFN beta-1a in direct viral defense, association of type I IFN deficiency with worse outcomes in COVID-19 (Hadjadj et al 2020, Zhang et al. 2020), and the induction of CD73-mediated preventive effects on endothelial barrier function and pulmonary capillary leak. The current study aims to detect the benefit of IFN beta-1a in clinical outcome measures (WHO 9-point ordinal scale), reduced need of mechanical ventilation, mortality and development of organ failure and ARDS versus the current standard of care for COVID-19. Dexamethasone was chosen as the comparator arm to align with treatment guidelines for hospitalized COVID-19 patients requiring supplemental oxygen. The rationale underlying the current design is provided below. Safety of both treatment arms will be assessed equally.

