### 3 STUDY OBJECTIVES

#### 3.1 Primary Objective

- To demonstrate the safety and tolerability of early IV IFN beta-1a administration in hospitalized patients with COVID-19 infection compared to dexamethasone
- To investigate the efficacy of IV IFN beta-1a to improve clinical status in hospitalized patients with COVID-19 compared to dexamethasone

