## 6.6 Safety Variables

### 6.6.1 Adverse Events

#### 6.6.1.1 Collection of Adverse Events

It is the responsibility of the Investigator to collect all AEs (both serious and non-serious) derived by observation, by spontaneous unsolicited reports of patients, and, where appropriate, by routine open questioning, e.g., "How have you felt since I last saw you?"

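### Most dexamethasone reactions the protocol names have no targeted collection, although safety compared with dexamethasone is a primary objective

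*Protocol*

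**What the plan says.** Protocol section 3.1 gives as the first primary objective: "To demonstrate the safety and tolerability of early IV IFN beta-1a administration in hospitalized patients with COVID-19 infection compared to dexamethasone". Section 4.1 also calls safety and tolerability the primary endpoint, and section 2.6 adds: "Safety of both treatment arms will be assessed equally".

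The expected reactions to each drug are listed in the background sections.

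- **IFN beta-1a** (sections 2.3.4 and 2.6): fever, anaemia, low platelets, raised liver enzymes, a fall in neutrophils, hypertension, rhabdomyolysis and flu-like symptoms.
- **Dexamethasone** (section 2.4.1): a "wide range of psychiatric reactions, psychotic reactions, behavioural disturbances, irritability, anxiety, sleep disturbances and cognitive dysfunction including confusion and amnesia", and then "decreased blood eosinophils and lymphocytes, increased infection susceptibility, masking of infection signs, aggravated infection, and fungal infections of mucous membranes and the skin". The same section puts severe reactions in adults at 5-6% and considers reactions tied to long-term use unlikely over six days.

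Scheduled measurements are vital signs (section 6.3.1 and Table 2) and the Table 3 laboratory panel. Its haematology part includes "Differential counts of: Neutrophils Eosinophils Basophils Lymphocytes Monocytes". Its biochemistry part reads "Albumin Creatine kinase Creatinine Bilirubin Alkaline phosphatase AST ALT Lactate Sodium (blood gas value acceptable) Potassium Bicarbonate Calcium", with no glucose. Samples are due pre-dose on D1, on D2-D7, D10 and D14, and on D28 or the last hospital day.

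All other adverse events are collected under section 6.6.1.1 by observation, spontaneous report and, where appropriate, open questioning of the kind "How have you felt since I last saw you". Section 6.6.1.3 adds that common laboratory changes, signs and symptoms in these inpatients need not count as adverse events unless they require intervention, stop study drug or concern the investigator.

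**The concern.** A comparative safety objective needs the characteristic harms of both drugs to be found with similar sensitivity. Here the IFN beta-1a harms are mostly vital signs and blood values that the schedule records in every patient. The dexamethasone harms are mostly symptoms and clinical states that someone must notice, mention or ask about. Section 2.6 justifies the blood count and differential by the neutrophil finding with IFN beta-1a; no section ties any measurement to the dexamethasone profile.

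Poor sleep, anxiety or mild confusion in a sick inpatient is easily put down to the illness, and the section 6.6.1.3 filter allows it to go unrecorded. At stake are the differences within these terms and any comparison of total treatment-emergent events.

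**Working it through.** The plan states no figure for safety, so there is none to reproduce. The check is a count of coverage, followed by illustrations of what under-recording does at the planned 70 patients per arm (section 7.4).

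**Step 1. Coverage of the named reactions**

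| Drug | Named reaction | Scheduled measurement |
|---|---|---|
| IFN beta-1a | Fever | Temperature (partial; see step 2) |
| | Anaemia, low platelets, neutrophil fall | Blood count and differential |
| | Raised liver enzymes | AST, ALT |
| | Hypertension | Blood pressure |
| | Rhabdomyolysis | Creatine kinase |
| | Flu-like symptoms other than temperature | None |
| Dexamethasone | Psychiatric, psychotic, behavioural, irritability, anxiety, sleep, cognitive (7) | None |
| | Eosinophil fall, lymphocyte fall (2) | Differential |
| | Infection susceptibility, masked infection, aggravated infection, fungal infection (4) | None targeted; temperature and white cells give indirect support |

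IFN beta-1a: 7 of 8 types have a scheduled measurement. Dexamethasone: 2 of 13 = 15%, leaving 11 of 13 = 85%. The second figure depends on how finely the list is split. By class there are three: blood cells are measured, infection is partly supported, and neuropsychiatric effects have nothing scheduled.

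**Step 2. The fever measurement**

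Section 2.6 says that in healthy volunteers temperature reached 38-39 °C at 1-2 hours after dosing and stayed up for about 2 hours. Table 2 takes vital signs pre-dose and at 30 and 60 minutes (±10 minutes) on D1-D6. The last post-dose reading therefore falls at the start of that window, and the schedule may miss part of the main IFN beta-1a reaction.

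**Step 3. Effect within one term**

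If a fraction *s* of events is recorded in both arms, the recorded difference is *s* × (p₁ − p₂). The ratio is preserved, but the difference and the counts shrink. Assume true rates of 20% and 10% and *s* = 0.5 (not in the documents):

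- True: difference 10 points; standard error √[(0.20×0.80 + 0.10×0.90)/70] = 0.0598; ratio 0.10/0.0598 = 1.67.
- Recorded: 10% against 5%, difference 5 points; standard error √[(0.10×0.90 + 0.05×0.95)/70] = 0.0443; ratio 0.05/0.0443 = 1.13.

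**Step 4. Effect on a pooled total**

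Suppose each drug causes its own reactions at the same true rate *r*, recorded with probabilities *s*_I (IFN beta-1a type) and *s*_D (dexamethasone type). The spurious gap is *r* × (*s*_I − *s*_D). With *s*_I = 1:

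| True rate *r* (assumed) | *s*_D = 0.75 | *s*_D = 0.50 | *s*_D = 0.25 |
|---|---|---|---|
| 5.5% | 1.4 points | 2.8 points | 4.1 points |
| 12.5% | 3.1 points | 6.2 points | 9.4 points |

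The 5.5% is the midpoint of the severe-reaction range in section 2.4.1. The 12.5% is the IFN beta-1a fever rate in the INTEREST trial (section 2.3.4). Both are borrowed for scale only. At 5.5%, expected recorded counts per 70 are 3.9 for IFN beta-1a against 2.9, 1.9 or 1.0 for dexamethasone.

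The sign is not fixed. If fever and flu-like symptoms are the ones missed, so that *s*_I = 0.50 and *s*_D = 0.75, the 5.5% row gives 5.5 × (0.50 − 0.75) = −1.4 points.

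**The case against.** The strongest reply is that both arms have the same schedule under double blinding, so the promise in section 2.6 is met literally. Tables by system organ class and preferred term (Protocol section 7.6.1, SAP section 6) compare like with like. This stands in part: there is no differential detection by arm within a term. It does not remove the dilution in step 3 or the possible distortion of pooled totals in step 4.

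General collection is also broader than it first looks. Section 6.6.1.1 gives three routes, so a reader who infers that everything rests on a single open question would be wrong. Examination covers neurological, skin, and ear, nose and throat findings and may be repeated under standard practice (section 6.3.2). Concomitant medications are recorded with their indication to D28 (section 5.7). These give partial cover, but none asks about sleep, mood or confusion.

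A reader might also infer that the comparison is tilted against IFN beta-1a. The documents do not show that. Detection rates are not given, post-dose vital signs end before the fever window closes, IFN beta-1a flu-like symptoms are equally unprompted, and the section 6.6.1.3 filter applies to laboratory values as well as symptoms.

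Nor do the documents support treating the missing glucose as a failure to measure a named reaction: section 2.4.1 does not mention hyperglycaemia. A clinically significant routine result could still be reported under section 6.6.1.3.4. Whether the panel changed when the comparator did cannot be checked, because the earlier panel is not available. Serious reactions would reach the data monitoring committee in any case (section 8.8).

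**Conclusion.** The asymmetry is real. Most named IFN beta-1a reactions have a scheduled objective measurement, while 11 of 13 named dexamethasone reactions depend on untargeted collection. The consequence is under-recording by event type, of unknown size and unproven direction. On the step 4 assumptions it amounts to a few percentage points in a pooled total at 70 per arm; at *r* = 5.5% with half recorded, about 2 patients. Much larger losses need reaction rates and detection rates that the documents do not supply.

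This is a worthwhile, inexpensive improvement to the protocol's design and does not show that the safety comparison is invalid. It has no bearing on inference in the reported trial: the SAP covers five patients, descriptively and without hypothesis tests.

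**What to change.** Add a short fixed list of prompts to the existing daily adverse event review and to the D14 and D28 calls, asked in both arms by blinded staff. It should cover sleep, mood or behaviour, confusion, and new or worsening infection (from section 2.4.1), together with the IFN beta-1a flu-like symptoms named in section 2.6. Including both drugs' reactions keeps the prompting symmetric; a list built from section 2.4.1 alone would create an imbalance the other way. In section 7.6.1, tabulate the prompted events by arm. If prompts are not added, state the limitation and qualify the sentence on equal assessment in section 2.6.

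As a secondary suggestion, record blood glucose at the existing chemistry time points, from the same sample or the routine result, and note that section 2.4.1 does not itself name hyperglycaemia.

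The cost is a few e-CRF fields, one table and, if glucose is taken up, one analyte without an extra draw. The downside is that prompting raises recorded adverse event counts in both arms, which makes comparison with unprompted historical rates harder.

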#### 6.3.4.2 COVID-19 confirmation test

A positive SARS-CoV-2 test result no older than 7 days should be available for inclusion in the study. The test can have been taken as part of the standard care or is performed for the study and the analyse method is according to the hospital laboratory routines. If information on the virus variant is available, it should be recorded in the e-CRF.

#### 6.3.5 Central Laboratory Assessments

A maximum of 73 mL of blood will be taken for study-specific testing during the study in addition to sampling for routine local analysis of haematology and biochemistry variables. One nasopharyngeal swab is taken for determination of SARS-CoV-2 variants.

##### 6.3.5.1 Anti-drug Antibodies to Interferon Beta-1a

For serum samples 5.0 mL of blood will be taken on D1 pre-dose (baseline) and D28 (or on last day in hospital or at withdrawal, if earlier) to determine the presence of anti-drug antibodies to IFN beta-1a.

Anti-drug antibody sample preparation and sample storage details are provided in the Laboratory Manual. It is essential that the actual time and date of collection of each antibody sample will be recorded in the sample collection form provided with the laboratory kits.

Anti-drug antibody samples will be analysed centrally at Wieslab AB, Malmö, Sweden.

##### 6.3.5.2 Myxovirus Resistance Protein A

Whole blood samples (2 mL) will be taken pre-dose on D1, D3, D5 and on D7 for hospitalized patients for analysis of MxA levels. For details of sample preparation and storage refer to the Laboratory Manual. MxA samples will be analysed centrally at Wieslab AB, Malmö, Sweden.

##### 6.3.5.3 Cluster of differentiation 73 (CD73), Potential Inflammatory Markers (PIMs) and Interferon Signalling Markers

Samples for the CD73 and PIM assessments will be collected pre-dose on D1 (baseline), D3, D5 and D7 for hospitalized patients as detailed in the Schedule of Procedures ([Section 6, Table 2](#)). Blood

samples of 2.5 mL will be collected for CD73; from these, serum samples will be prepared for the testing. Blood samples of 6.0 mL will be collected for PIM sample preparation; from these, plasma and cell samples will be prepared for the testing of the potential inflammatory markers, interferon signalling markers and genetics. Sample preparation and storage details are provided in the Laboratory Manual. It is essential that the actual time and date of collection of each sample is recorded in the sample collection form provided with the laboratory kits.

CD73 samples will be analysed centrally by Wieslab AB, Malmö, Sweden.

PIMs may include (but are not limited to): Interleukin-6, Interleukin-8, von Willebrand Factor, Hypoxia-inducible factor 1-alpha, Angiopoietin-2, IFN- $\gamma$ , IP-10, MCP-1, and TNF- $\alpha$ , and interferon signalling markers. Inflammatory markers and interferon signalling will be analyzed both on a protein and RNA expression level using plasma and peripheral blood mononuclear cells (PBMCs) using Nanostring analyses. Inflammatory markers will be analysed at MediCity Research Laboratory, University of Turku, Turku, Finland. Nanostring analyses will be performed at Wake Forest University Medical School after RNA and DNA extraction has been performed at MediCity for pharmacogenetics (see below).

